#### 4.3.3 Accompanying examinations:

**Planned measures:** These will take place at the time of study enrollment/before the start of radiation therapy, in parallel with radiation therapy, at the time of completion of radiation therapy and during the follow-up.  
Study visits.

**Implementation:** Follow-up visits are planned for the following times:

1. Pre-therapeutic for study inclusion and status assessment before the start of therapy (radiation of the prostate and metastases); six (up to a maximum of 9 months) after initiation of systemic therapy with evidence of a PSA value of  $>0.2$  ng/ml.
2. At the time of completion of therapy (radiation of the prostate and metastases).  
3rd month 1, 3, 6, 9, 12, 15, 18, 21 and 24 after study enrollment.

4. Subsequently, follow-up examinations are conducted as personal visits every 3 months to 18 months after completion of metastasis-directed therapy to record PSA levels, quality of life and to inquire about possible side effects.

**Specific burdens:** Attending study visits involves a time commitment, including travel to and from the study center and the visit itself, which lasts approximately 30-45 minutes. If the PSA level is checked in the patient's outpatient setting at the time of visits not related to the discussion of PSMA-PET findings, the questionnaires can be sent by mail. In this case, approximately 30 minutes should be allocated for completing the questionnaires per visit. The PSA level is checked via blood draw, which involves venipuncture. Theoretically, this procedure carries a risk of bleeding, infection, or tissue injury. However, blood draws with PSA level checks every 3 months are already part of routine urological therapy monitoring and are not an additional measure within the study.

**Benefit:** Regular study visits ensure close monitoring with consistent, frequent check-ups of PSA levels, a surrogate parameter for cancer progression. If PSA levels rise, appropriate diagnostic procedures can be initiated immediately, and any new findings can be investigated and treated. Medical consultations and assessments of quality of life allow for the initiation of appropriate therapy in cases of quality of life limitations or the occurrence of side effects. Furthermore, patients have reported that they appreciate and value a consistent connection to their treatment center.

#### 4.4 Sample Size Estimation and Recruitment Period Based on existing

publications regarding PSA response to complete androgen blockade and irradiation of bone metastases, a radiological response after RECIP with a PSMA volume reduction of at least 30% is expected to be achieved in 40% of patients through the study intervention. If the success rate remains below 15%, it is assumed that the therapy provides no benefit. The study hypothesis will be rejected with a sample size of 27 patients (power of 90%, one-sided significance level  $\alpha=0.05$ ) if  $>5/27$  patients do not show a response after RECIP 12 months following metastasis-directed therapy.

At the urological center in Tübingen, approximately one patient per week with a new diagnosis of primary bone metastases in prostate cancer is presented to the tumor board. Considering the expected inadequate treatment response in approximately 20-30% of cases and adhering to the inclusion and exclusion criteria, a realistic number of 5-10 patients per center could be enrolled within one year. Therefore, a recruitment period of 12 months was chosen for the target of 6 centers.

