Aim of the Study	
Pilot study on radiological response after RECIP in PSMA-PET/CT in patients with primary metastatic prostate cancer Carcinoma, which occurs after 6 months in cases of oligopersistence
 
Systemic therapy administered as part of local ablative radiotherapy can be.
 
If the primary endpoint is reached, a multicenter study is planned, with an application for external funding (e.g., cancer support).

Objectives/Endpoints
 
 
• Primary Objective/Endpoint
 
• Secondary Objective/Endpoints
 
• Exploratory Objective
 
	
Primary endpoint: Response in PSMA-PET/CT after RECIP with a decrease in PSMA volume of at least 30%.
 
Secondary endpoints and parameters collected:
 
 
• PSA progression
 
• Lesion-specific response of the irradiated area Lesions on PSMA-PET/CT
 
• Objective response rate (ORR)
 
• Interval until change of systemic therapy
 
• Overall Survival (OS)
 
• Failure-free survival (FFS) as any disease-specific Event
 
• Progression-free survival (PFS)
 

	
 
Distant metastasis-free survival (MFS)
 
Disease-specific survival (prostate cancer specific survival, PCS)
 
 
Exploratory endpoints:
 
 
Reason for changing systemic therapy
 
Choice of the next systemic therapy line
 
Side effects (according to CTCAEV5 and RTOG), Quality of life (EORTC QLQ-C30 prostate, QLQ-PR25, EQ-D5), assessment of organ function (gastrointestinal and urogenital: IPSS score, ICIQ score, NCI-PRO-CTCAE, IIEF)
 

Statistics, Safety Variables and Stopping Rules	
Study design: Single-arm phase II study using the Fleming design
 
Number of cases: 27 patients
 
Statistical estimation: Significance level <math>p=0.05</math>; Null hypothesis: Success rate <math><15\%</math>, effectiveness of the intervention is certain if success rate <math>>40\%</math>, Power <math>90\%</math>.
 
Stopping rules: CTCAE grade 4 and 5 attributable to the therapy performed; persistent grade 3 adverse events <math>> 90</math> days after radiation therapy in <math>>50\%</math> of patients.

Database	
Database: REDCap
 
Biometrics: IKEaB, [name]

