## 4. Description of the clinical study

### 4.1 Study design and rationale

This study is a non-randomized, single-stage phase II trial with a Fleming design. No control group is included because both ablative radiotherapy of metastases and (ultra-)hypofractionated radiotherapy of the prostate are standard treatment in curative and limited metastatic disease settings and have been validated in independent studies [11, 12, 24].

Several studies have demonstrated the benefit of MDT even in cases of polymetastatic disease, with a well-tolerated side effect profile [15, 16, 23, 25]. In a single-center series where patients with bone metastases, with and without prior prostate therapy, received ablative MDT plus antiandrogen therapy, a 2-year progression-free survival (PFS) was achieved in 40% of patients. Three-quarters of patients who experienced recurrent bone metastases received MDT again, thus delaying the need to switch systemic therapy. No high-grade adverse events (CTCAE grade 3 or higher) were observed with MDT.

The ultrahypofractionated radiotherapy of the prostate in this study is planned analogously to the PACE-B trial. In that trial, non-metastatic patients received primary radiotherapy of the prostate with 36.25 Gy/40.0 Gy to the PTV/CTV in five fractions with a single dose of 7.25 Gy/8.0 Gy. The 5-year toxicity analysis showed no increase in side effects with ultrahypofractionation in primary radiotherapy of the prostate compared to the normofractionated standard of care with 78 Gy [26]. Furthermore, the present study omits the administration of a prostate boost, thus limiting the single dose to 7.25 Gy and the total dose to 36.25 Gy. As an alternative treatment regimen (in case of technical or medical contraindication to ultrahypofractionation, radiation therapy with moderate hypofractionation with 20 x 3 Gy single dose (analogous to the CHHiP trial [27]) or radiation therapy according to departmental standard, e.g. analogous to the STAMPEDE study with 6 x 6.0 Gy) is performed.

[figure not shown]
The STAMPEDE study, which investigated the effect of PDT in combination with standard-of-care therapy in patients with primary metastatic disease, demonstrated a benefit in overall survival from local therapy of the prostate in cases of limited metastasis [11].

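### The section 4.4 decision rule (more than 5 of 27 without response) does not match its own design under any reading; only a cut-off of at least 8 responders does.

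*Protocol*

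**What the plan says.** Section 4.1 sets the design: "This study is a non-randomized, single-stage phase II trial with a Fleming design". Section 4.4 supplies the inputs. A RECIP response (PSMA volume reduction of at least 30%) "is expected to be achieved in 40% of patients through the study intervention". The no-benefit limit is given as "If the success rate remains below 15%, it is assumed that the therapy provides no benefit". The error rates are "power of 90%, one-sided significance level" 0.05.

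The decision sentence follows: "The study hypothesis will be rejected with a sample size of 27 patients" if more than 5 of 27 "patients do not show a response after RECIP 12 months following metastasis-directed therapy". The section does not say whether the study hypothesis is the efficacy claim or the null.

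No other section gives a count. The statistics row of the synopsis ("Null hypothesis: Success rate" below 15%, effective above 40%) repeats the rates, alpha, power and number of patients, and is not itself in error. Section 3.1 gives only the 40% target. Section 8.3 describes estimates with 95% confidence intervals, for both the intent-to-treat and per-protocol populations, and has no cut-off.

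**The concern.** A single-stage design with 27 patients and a 15% null should declare success at some number of responders a little above 27 × 0.15 = 4.05. The sentence in 4.4 counts non-responders instead, and uses a number, 5, that is close to the null expectation for responders. The direction and the count both look wrong.

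This rule decides whether the primary endpoint is met. The synopsis and section 3.3 make the follow-on trial depend on that, and section 2.4 says the combination will then be offered routinely. If the rule is settled only after the scans are read, any correction will look driven by the data.

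**Working it through.** **Inputs.** Section 4.4: null rate p0 = 0.15, target rate p1 = 0.40, n = 27, one-sided alpha 0.05, power 0.90. X is the number of responders, X ~ Bin(27, p). For a rule 'success if X ≥ r':

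- alpha = P(X ≥ r | p = 0.15)
- power = P(X ≥ r | p = 0.40)

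**Step 1: the plan's sample size.** A search over n for the smallest exact design with alpha ≤ 0.05 and power ≥ 0.90 gives n = 27 with r = 8. The planned 27 is reproduced. Fleming's normal approximation points to the same cut-off: 27 × 0.15 + 1.645 × √(27 × 0.15 × 0.85) = 4.05 + 1.645 × 1.855 = 7.10, so r = 8.

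**Step 2: cut-offs at n = 27.**

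| Success if responders ≥ | alpha at 15% | power at 40% |
|---|---|---|
| 6 | 0.2097 | 0.9845 |
| 7 | 0.0986 | 0.9579 |
| 8 | 0.0398 | 0.9047 |
| 9 | 0.0138 | 0.8161 |

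Only r = 8 meets both requirements. The exact one-sided 95% lower limits agree: 10.1% for 6/27, 12.9% for 7/27 and 15.7% for 8/27. Only the last is above 15%.

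**Step 3: the sentence as written, study hypothesis = efficacy.** More than 5 non-responders means failure, so success requires at most 5 non-responders, that is at least 27 − 5 = 22 responders (22/27 = 81%).

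| True response rate | P(X ≥ 22) |
|---|---|
| 40% | 0.000013 |
| 60% | 0.015 |
| 70% | 0.136 |
| 80% | 0.539 |

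**Step 4: the sentence as written, study hypothesis = null.** The null would be rejected with 6 or more non-responders. At a true rate of 15% the non-responders follow Bin(27, 0.85), and P(at least 6) differs from 1 by less than 10⁻¹². An ineffective therapy would practically always pass.

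**Step 5: the 'not' deleted.** Success with more than 5, that is at least 6, responders: alpha 0.2097, power 0.9845. Reading the sentence as 'fails if 5 or fewer respond' gives the same boundary and the same alpha. At the null boundary this is 0.2097/0.05 = 4.2 times the stated level.

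**Step 6: missing scans.** If a patient without an evaluable scan counts as a non-responder and the cut-off stays at 8, one missing scan leaves 26 possible responders (alpha 0.0321, power 0.878). Two leave 25 (alpha 0.0255, power 0.846).

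**The case against.** The best defence is that the text is a translation. The bladder appears as a bubble in the constraint tables, PDT is expanded as photodynamic therapy in section 2.4 although the abbreviation list defines it as treatment of the primary, and comparison signs are damaged in section 6.7. The 'not', and even the '>', may not be what the authors wrote, and a team planning on 40% is unlikely to demand 22 of 27 responders. That stands as far as the direction goes, so the inversion should not carry the point alone. It does not rescue the number: a reader who repairs the direction by common sense arrives at 6 responders, not 8.

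It could also be said that the analysis plan will set the rule. A missing rule could be left to it. This one is stated, and a correct rule elsewhere would contradict the protocol.

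A reader might infer two stronger claims. One is that the rule as written gives the wrong answer at every plausible response rate. It does not: under the efficacy reading it correctly fails a therapy at 15%, and it passes one at 80% in 54% of trials. The other is that a cut-off of 6 would pass one in five ineffective treatments. The 0.210 holds only at a true rate of exactly 15%; the probability is 9.7% at 12%, 4.7% at 10% and 0.2% at 5%.

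**Conclusion.** The concern holds. The stated rule is wrong as written, and no reading of 5/27 yields one-sided alpha 0.05 with 90% power for 15% against 40%. Taken literally, it either fails a therapy at the 40% target almost every time or passes a therapy at 15% almost every time, depending on what the study hypothesis means. With the negation removed, the maximum type I error is 0.210 instead of 0.05. The sample size of 27 is correct and itself implies a cut-off of 8.

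The calculation assumes independent patients with a common response rate, an exact binomial test and 27 patients in the count. The documents do not show which direction the authors intended. The conclusion does not depend on that, because the number fails in either direction.

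**What to change.** Replace the decision sentence in section 4.4 with:

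*The null hypothesis (response rate at most 15%) is rejected if at least 8 of 27 patients show a RECIP response 12 months after metastasis-directed therapy. With 7 or fewer responders the therapy is not considered sufficiently active (exact one-sided alpha 0.040, power 90.5% at 40%). Patients in the ITT population without an evaluable scan count as non-responders. This one-sided test, not the two-sided 95% interval of section 8.3, decides the primary endpoint.*

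The last clause is needed because the exact two-sided 95% lower limit for 8/27 is 13.8%, below 15%, so a reader using that interval (if it is two-sided) could reach the opposite conclusion at the cut-off. Add the same count to the synopsis, which gives none.

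The cost is one short passage in section 4.4 and one line in the synopsis, with no change to sample size, schedule or treatment. The downside is some loss of power if scans are missing: 0.878 with one missing and 0.846 with two.

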#### 4.5 Participating trial centers and investigators

The study will be conducted as a multicenter trial. A collaboration with Ludwig Maximilian University of Munich already exists; collaborations with the following study centers are planned: University Hospital Freiburg, University Hospital Augsburg, Carl Gustav Carus University

Dresden and the University Hospital of Cologne. A principal investigator and a deputy will be appointed for each site. The study protocol presented here will be submitted to the ethics committees of the cooperating centers as soon as an unconditional ethics opinion has been received from the Ethics Committee of the Medical Faculty of Tübingen. Patient recruitment will take place at the respective sites after a positive ethics opinion from the local ethics committee.

## 5. Patient selection

### 5.1 Recruitment

Patients for the study are referred to the outpatient clinic of the University Hospital for Urology, the urological tumor board, and their primary treating urologists to the outpatient clinic of the University Hospital for Radiation Oncology (or the cooperating radiation therapy centers) for an initial consultation and screening for potential study participation. During this consultation, patients are first informed about the guideline-based therapy – i.e., monotherapy with MDT in the event of symptoms (pain, risk of postural instability, etc.). All patients of the University Hospital for Radiation Oncology in Tübingen who meet the inclusion criteria are offered participation in the study.

The procedure, possible additional burdens caused by radiation therapy, any side effects, and the potential benefits for the patient are explained in detail.

It is specifically pointed out that participation in the study is voluntary and that consent can be withdrawn at any time before or after therapy. However, for radiobiological reasons, radiation therapy should ideally not be interrupted once started; this is possible, however, if the patient explicitly requests it after receiving appropriate information. It is also emphasized that guideline-compliant follow-up care and any potential re-irradiation in the event of symptomatic metastasis would be affected by a possible discontinuation of the RIALTO study.

becomes.

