## 5.5 Patient discharge

Patients included in the study can withdraw from the study at any time at their own request and without giving reasons, and without affecting any future treatment or regular follow-up care after radiation therapy.

Exclusion from the study may occur at the discretion of the study physician for reasons of health risk (for example, if a serious comorbidity is present or if the planned radiation therapy is not possible due to prior radiation treatment). In the event of withdrawal from the study, the reason will be documented in the respective patient file and in the eCRF (CRF Drop-Out).

All patients who prematurely withdraw from the study after having already undergone a study intervention should receive a final examination immediately upon withdrawal, which should be documented in the eCRF (CRF Follow-Up). Furthermore, they should be offered a connection to the center as part of their regular radiotherapy follow-up care.

If consent to participate in the study is withdrawn, no further clinical data will be collected and no further study visits will be conducted. If a study intervention has already taken place, continued contact with the center for routine follow-up care after radiotherapy will be offered; no study data will be collected during this follow-up, only routine radiotherapy follow-up care will be provided. All data collected up to this point will be anonymized immediately, unless a request for complete data deletion is received. Treatment plans for treatments already administered within the study must be retained for 30 years in accordance with radiation protection regulations.

A cancellation of the planned study measures may become necessary for the following reasons:

- Disease progression necessitating the initiation of chemotherapy (e.g. Occurrence of visceral metastasis).
- Deterioration of general health, which precludes the continuation of the planned Measures prevented.
- An increase or doubling of the PSA level compared to baseline that is not attributable to a lesion requiring local therapy and necessitates a change in systemic therapy. If PSA progression according to Phoenix criteria is present, the next scheduled PSMA-PET scan is prioritized, and if isolated metastases are found, stereotactic radiotherapy is performed again. In cases of diffuse progression or the presence of visceral metastases, the therapy is adjusted according to the tumor board of the respective center.

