#### 9.3 Legal radiation protection requirements

The requirements of radiation protection according to the Radiation Protection Ordinance and the Radiation Protection Act must be observed at all times during the diagnostic and therapeutic procedure.

This also includes the obligation to provide aftercare.

The diagnostic and therapeutic measures planned in the study have been validated in studies and are performed in routine clinical practice. Furthermore, in a position paper, the German Society for Radiation Oncology (DEGRO) has defined hypofractionated radiotherapy for prostate cancer as a medical procedure, provided certain conditions are met. This definition also includes the irradiation of patients with metastatic disease. These conditions are met. Moreover, the study protocol has been submitted to the DEGRO expert committee. The DEGRO expert committee's statement classifying the procedure as a therapeutic radiation application within the scope of medical practice is included with the study protocol (see appendix). Therefore, the study does not involve the application of ionizing radiation to humans for the purpose of medical research as defined in Section 31 of the German Radiation Protection Act (StrSchG), and consequently, no application needs to be submitted to the Federal Office for Radiation Protection (BfS). Since the PSMA-

PET/CT examinations are performed at defined times; the planned PSMA-PET/CT examinations are reported to the BfS.

**9.4 Patient Information and Consent Form** Before enrollment in the prospective study, each patient is informed that participation is voluntary and that withdrawal during the observation phase is possible at any time without explanation and without any negative impact on further care and therapy. In this case, therapy will continue as standard treatment without further modifications.

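### Section 5.1 says leaving the study would affect follow-up care and re-irradiation of symptomatic metastases; Sections 5.5 and 9.4 say withdrawal does not affect care

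*Protocol*

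**What the plan says.** Three places in the protocol describe what happens to a patient's care on leaving the study.

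- **Section 5.1 (Recruitment)** describes the first consultation. It says the patient is told that "participation in the study is voluntary and that consent can be withdrawn at any time before or after therapy". It adds that radiotherapy, once begun, should ideally not be interrupted, although it can be at the patient's explicit request. It then says staff also emphasise that "guideline-compliant follow-up care and any potential re-irradiation in the event of symptomatic metastasis would be affected by a possible discontinuation of the RIALTO study". A single orphaned word, *becomes*, stands on its own line after that sentence.
- **Section 5.5 (Patient discharge)** says patients can withdraw at any time, without giving reasons, and "without affecting any future treatment or regular follow-up care after radiation therapy". For a patient who withdraws consent after a study intervention, it adds that "continued contact with the center for routine follow-up care after radiotherapy will be offered".
- **Section 9.4 (Patient Information and Consent Form)** says each patient is informed before enrolment that "withdrawal during the observation phase is possible at any time without explanation and without any negative impact on further care and therapy". It continues: "In this case, therapy will continue as standard treatment without further modifications".

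**The concern.** Sections 5.1 and 9.4 both describe what a patient is told before agreeing to take part, and Section 5.5 sets out what happens when a patient leaves. On the consequence of leaving, 5.1 points one way and the other two point the other. Staff who follow the protocol literally would give a patient two incompatible statements.

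What is at stake is voluntariness. The 5.1 sentence sits in the paragraph on voluntary participation and is something staff are to stress. Eligible patients had at least four bone metastases at diagnosis (Section 5.2), so symptomatic bone disease is a real prospect for them. Section 5.1 itself counts metastasis-directed treatment in the event of symptoms as part of guideline-based therapy. Being told that leaving would affect such care could act as pressure to stay.

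**Working it through.** No figure in the plan depends on this point, so there is nothing to recalculate. The check is a comparison of the texts.

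1. **Is there a negation in the 5.1 sentence?** No. As printed it is a complete, affirmative statement that follow-up care and re-irradiation would be affected.

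2. **Does it concern the individual patient leaving?** The phrase about discontinuation of the study could, in isolation, mean that the whole trial ends. The surrounding sentences concern voluntary participation, withdrawal of consent and interruption of radiotherapy at the patient's request. Termination of the trial is handled separately in Section 5.7. The individual reading is the natural one.

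3. **Do the sections cover the same care?**

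| Item | 5.1 | 5.5 | 9.4 |
|---|---|---|---|
| Follow-up care | would be affected | not affected; routine follow-up still offered after an intervention | no negative impact on further care |
| Later treatment, including re-irradiation for symptoms | would be affected | future treatment not affected | no negative impact on further therapy; continues as standard treatment |

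   Both kinds of care named in 5.1 fall within what 5.5 and 9.4 say is unaffected.

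4. **Are 5.5 and 9.4 equally broad?** Not quite. Section 9.4 speaks of withdrawal during the observation phase and of no *negative* impact, which is slightly narrower. Section 5.5 has no such limit, so the conflict with 5.1 stands on 5.5 alone.

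5. **Could 5.1 simply mean that study visits stop?** Section 5.5 does say that, after consent is withdrawn, study visits and data collection end. But 5.1 names guideline-compliant follow-up care, not study visits, and 5.5 keeps routine follow-up apart from study follow-up. This reading does not remove the conflict.

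6. **How far does it reach?** Section 5.1 describes the conversation held with every recruited patient, so all 27 planned. Section 4.4 targets six centres, and Section 4.5 says this protocol is to go to the ethics committees of the cooperating centres.

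**The case against.** The strongest reply is that this is damage from translation or editing and not a rule anyone intended. The orphaned *becomes* looks like a displaced clause-final verb, and a negation is easily lost at such a break. Similar damage occurs elsewhere: the bladder appears as *bubble* in the organ-at-risk tables, and the visit schedule in Section 7.1 is still in German. Sections 5.5 and 9.4 agree with each other, and 5.1 itself affirms that consent can be withdrawn at any time. Nothing shows that any site works from this English sentence. Most of this stands. A lost negation is the likely cause, although the source-language wording is not available to confirm it. It explains the conflict without removing it from the protocol as it reads.

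Two stronger inferences are tempting and are not supported.

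- A reader might infer that a patient who leaves loses, or is no longer assured of, palliative re-irradiation. Section 5.1 says care would be affected; it does not say that it is refused, withdrawn or unassured.
- A reader might infer that patients kept in the study against their will would distort the quality-of-life results. Nothing in the protocol establishes that chain. Quality of life is also listed only among the exploratory endpoints.

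**Conclusion.** The inconsistency is real and minor. Section 5.1 states a consequence of leaving the study that Sections 5.5 and 9.4 contradict, in text that describes what patients are told before consenting. It touches the information given to all 27 planned patients, but has no effect on sample size, endpoints or analysis. It does not show that any patient's access to care is at risk.

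The conclusion assumes that the 5.1 sentence refers to an individual patient leaving, which its context favours. If it referred to termination of the trial, patients would still be told that guideline-based care depends on the study, and the sentence would still need clarifying. The patient information sheet is not available, so whether it carries the same wording is unknown.

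**What to change.** Check the sentence in Section 5.1 against the source-language protocol. Then reconcile it with Sections 5.5 and 9.4 so that all three state the same consequence of withdrawal for follow-up care and for re-irradiation of symptomatic metastases, and make clear that the sentence is about a patient leaving and not about the trial ending. Remove the stray word that follows it. Check the patient information sheet for the same statement before further centres use it.

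The cost is one sentence and one document check. If only the English version is wrong, correcting the translation may be enough. If the source text carries the same sentence, the change must be communicated to the ethics committee under Section 9.1 and approved as an amendment under Section 10.2.
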